##### Exclusion Criteria

1. Receiving only low flow oxygen therapy less than or equal to 15L/min
2. More than two doses of corticosteroids (oral or IV, at any dose) received any time during the previous 14 days prior to screening
3. Existing indication for corticosteroids
4. High suspicion for/or confirmed COVID infection
5. Acute traumatic brain injury during the index hospital admission
6. Allergy to dexamethasone

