##### **Extended Cohort**

##### Inclusion Criteria

1. Are admitted to an ICU
2. Have already received a short course (defined below) of corticosteroid specifically for acute respiratory failure, this will include patients:

- a. randomized to corticosteroid arm in Early Cohort and completed 10 days of corticosteroid as per Early Cohort protocol
  - b. patients with COVID who have received between 8-12 days of corticosteroids as standard of care
  - c. others who have received between 8-12 days of corticosteroids for AHRF
- OF NOTE: the initial corticosteroid does not have to be dexamethasone and corticosteroids can be at any initial dose
3. Ongoing AHRF requiring HFNC, NIV (continuous positive airway pressure [CPAP] or bilevel) or invasive ventilation

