### **Analyses**

Any deviation from the original statistical plan will be described in the final report.

[figure not shown]

All analyses, interim and final, will use the intention-to-treat principle. The baseline characteristics comparing randomized groups will be reported using means (and standard deviations), medians (and interquartile ranges) or proportions. Trial data will be analyzed using Bayesian hierarchical generalized linear models to estimate the posterior probability of superiority (or inferiority) and equivalence for each intervention within each domain. The hierarchical model will account for centre, time period, sex and oxygen support at the time of randomization (HNFC, NIV, invasive mechanical ventilation or ECLS). Posterior probability distributions will be computed by combining the likelihood function with minimally informative priors and updated every three months as information (observations) accumulate in the trial. Statistical analysis will be adjusted for whether a patient was enrolled in one CORT-E cohort or both CORT-E cohorts. We do not expect interaction between CORT-E and the other PRACTICAL domains. The final study analysis, separate for each cohort, will be completed once either superiority, inferiority or equivalence has been observed and confirmed by the DSMB and Platform Steering Committee.

We will collect sex and perform subgroup analysis based on this variable. It is less feasible to collect gender as most patients will not be conscious at the time of enrolment. We don't expect effect modification for either cohort based on sex or gender. Understanding the CORT-E eligibility criteria, we plan to enroll a diverse population of patients representative of the demographics of ICU patients presenting at the participating sites.

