As above, in keeping with the Bayesian framework, frequent reassessments of posterior distribution will occur. We plan to perform these analyses after each 200 patients have been randomized (after we have primary outcome data for each 200 patients). We will not start these interim analyses until at least 750 patients have been enrolled (again, until we have outcome data for at least 750 patients) in each domain in order to decrease the likelihood of spurious early findings based on an insufficient number of observations. These analyses will remain blinded to all study investigators and will be reviewed only by the DSMB. If stopping criteria are met, the DSMB may suggest stopping enrolment to one or both cohorts. The stopping criteria are intentionally conservative to avoid inappropriately stopping the trial early.

Six subgroups apply to both cohorts: 1) patients < 65 versus  $\geq$  65 years (hypothesizing that younger patients will benefit more from early and extended corticosteroids); 2) patients requiring HFNC or NIV versus invasive mechanical ventilation at the time of randomization (hypothesizing that patients receiving invasive ventilation will benefit more from early and extended corticosteroids); 3) male vs. female sex (hypothesizing no difference); 4) those requiring ECLS at baseline versus not requiring ECLS (hypothesizing that those requiring ECLS will benefit more

from early and extended corticosteroids; and 5) patients requiring versus not requiring vasopressor support at randomization (hypothesizing that those requiring vasopressor support will benefit more from early and extended corticosteroids). Two subgroups will apply exclusively to Extended Cohort 1) patients with COVID versus those with non-COVID AHRF (hypothesizing that those with COVID will benefit more from extended corticosteroids), 2) patients enrolled only in Extended Cohort versus those enrolled in both Early Cohort and Extended Cohort (to assess for interaction between cohorts). We will collect plasma samples at baseline to allow for post-hoc subgroup analysis for Early Cohort and Extended Cohort based on inflammatory groups (hypothesizing that those with elevated inflammatory markers [IL-6, sTNFr1 and IL-8] will benefit more from corticosteroids). We will perform these subgroup analyses only for the primary outcome.

[figure not shown]

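### The Extended Cohort subgroup meant to detect interaction between cohorts is partly confounded with COVID status

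*Protocol*

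**What the plan says.** The Analyses section lists two subgroups that apply to the Extended Cohort alone. The first is "patients with COVID versus those with non-COVID AHRF (hypothesizing that those with COVID will benefit more from extended corticosteroids". The second is "patients enrolled only in Extended Cohort versus those enrolled in both Early Cohort and Extended Cohort (to assess for interaction between cohorts". The section neither restricts the second comparison to non-COVID patients nor links it to the first.

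The eligibility criteria determine who can be in each group. The Early Cohort exclusions include "High suspicion for/or confirmed COVID infection". The Extended Cohort admits three kinds of patient:

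- "randomized to corticosteroid arm in Early Cohort and completed 10 days of corticosteroid as per Early Cohort protocol"
- "patients with COVID who have received between 8-12 days of corticosteroids as standard of care"
- "others who have received between 8-12 days of corticosteroids for AHRF"

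On modelling, the Analyses section says "The hierarchical model will account for centre, time period, sex and oxygen support at the time of randomization". It adds an adjustment for enrolment in one cohort or both. COVID status is not among the listed terms, although footnote 3 of the Study Assessment Schema has it collected at baseline.

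**The concern.** The second subgroup is given one purpose: to show whether the two cohorts interact. Its two groups differ not only in enrolment history but also in COVID status, and the protocol itself names COVID as an expected modifier of the extension effect. A difference caused by COVID would then be read as an effect of having been in the Early Cohort. Conversely, a real effect of enrolment history could be offset by a COVID difference in the other direction and go unseen.

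An adjustment for one versus both enrolment is a main effect. It shifts baseline risk and does not separate two effect modifiers. A COVID main effect would fail for the same reason.

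**Working it through.** **Step 1. Set the eligibility routes against the subgroup.**

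| Route into the Extended Cohort | COVID status | Subgroup |
|---|---|---|
| Completed the Early Cohort corticosteroid arm | Non-COVID by exclusion | Both cohorts |
| COVID, 8–12 days of standard-of-care corticosteroid | COVID | Extended-only |
| Others, 8–12 days of corticosteroid for AHRF | Non-COVID | Extended-only |

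The overlap is partial: the third route supplies non-COVID patients to the Extended-only group. Two exceptions should be rare. One is COVID recognised after Early Cohort randomisation. The other is an Early Cohort control patient given open-label corticosteroid who later qualifies by the third route; the protocol expects few crossovers (Participant Compliance and Dropout).

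**Step 2. Size of the distortion.** The protocol gives no figure for this subgroup, so there is none to reproduce. The inputs below are assumptions: control mortality *p*, extension odds ratios OR_C (COVID) and OR_N (non-COVID), and COVID share *c* of the Extended-only group. Enrolment history is given no effect, so the true ratio of odds ratios is 1.

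- Control odds: o = p/(1 − p)
- Treated risk: risk(OR) = OR·o/(1 + OR·o)
- Extended-only treated risk: r = c·risk(OR_C) + (1 − c)·risk(OR_N)
- Extended-only OR: OR_E = [r/(1 − r)]/o
- Apparent ratio, both cohorts over Extended-only: OR_N/OR_E

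Worked case with p = 0.40, OR_C = 0.65, OR_N = 0.90, c = 0.5:

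- o = 0.40/0.60 = 0.667
- risk(0.65) = 0.433/1.433 = 0.302; risk(0.90) = 0.600/1.600 = 0.375
- r = 0.5 × 0.302 + 0.5 × 0.375 = 0.339, odds 0.512
- OR_E = 0.512/0.667 = 0.768
- Apparent ratio = 0.90/0.768 = 1.17

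At c = 0.3 and 0.7, OR_E is 0.819 and 0.719. When control risk differs by COVID status, the control risk of the Extended-only group is mixed in the same way. Results:

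| Assumptions | Apparent ratio at COVID share |
|---|---|
| p 0.40; OR_C 0.65, OR_N 0.90 | 30%: 1.10; 50%: 1.17; 70%: 1.25 |
| p 0.40; OR_C 0.75, OR_N 1.00 | 30%: 1.09; 50%: 1.15; 70%: 1.22 |
| p 0.35; OR_C 0.75, OR_N 1.00 | 10%: 1.03; 25%: 1.07; 50%: 1.15; 75%: 1.24 |
| p 0.35; OR_C 0.70, OR_N 0.90 | 10%: 1.02; 25%: 1.06; 50%: 1.13; 75%: 1.20 |
| p 0.30 non-COVID, 0.45 COVID; OR_C 0.75, OR_N 1.00 | 10%: 1.03; 25%: 1.08; 50%: 1.16; 75%: 1.25 |
| OR_C = OR_N = 1.00 (no modification) | 1.00 at every share |

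**Step 3. Chance of a false signal.** A simulation used 2000 Extended Cohort patients (the planned maximum), 1:1 allocation, p = 0.35, OR_C = 0.75, OR_N = 1.00, 20% or 40% of patients coming from the Early Cohort, a flat prior with a normal approximation, and 20,000 replicates per setting. It recorded how often the posterior probability of a spurious interaction, in the direction of more benefit in the Extended-only group, reached 0.975. The nominal rate is 0.025.

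| COVID share of Extended-only | As planned | Non-COVID only |
|---|---|---|
| 25% | 0.049–0.055 | 0.024–0.025 |
| 50% | 0.085–0.110 | 0.024–0.026 |
| 75% | 0.146–0.192 | 0.024–0.026 |

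With restriction to non-COVID patients, the simulated ratio of odds ratios returned to 1.00 (0.998 to 1.002).

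**The case against.** The strongest reply is that the protocol names a partition and a purpose, not a model. Treatment-by-COVID is already a planned subgroup, and the synopsis refers further detail to the PRACTICAL Master SAP, which I have not seen. That plan may fit both interactions together. This stands in part: if it does, only the stated purpose needs changing. But the protocol fixes the contrast and how it is to be read, and as written that reading does not follow.

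Second, the distortion needs COVID to modify the extension effect. The protocol only hypothesises this, and its background reports a meta-analysis of corticosteroids in ARDS that was consistent across COVID and non-COVID causes. It also allows for a waning pandemic, and so for a low COVID share. All of this stands. A reader might infer that the subgroup definition alone produces a false interaction; it does not, as the rows with no modification and with a 10% share show.

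Third, a reader might infer that the trial's whole protection against carry-over between cohorts rests on this comparison. The protocol does not support that: stopping triggers and final analyses are separate by cohort, and enrolment in one or both is adjusted for. Extended Cohort patients are also freshly randomised, so the treatment effect within each subgroup is not confounded. Only the explanation of a difference between subgroups is in doubt.

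Fourth, a reader might fault the contrast for not comparing prior corticosteroid with none. The protocol does not claim that it does, since every Extended Cohort patient must already have had a course.

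**Conclusion.** The concern holds in a limited form. The comparison of Extended-only patients with those in both cohorts is partly confounded with COVID by the eligibility criteria, and the protocol's own hypothesis gives the direction of the resulting distortion. On the scale of the ratio of odds ratios, the distortion runs from about 2–3% at a 10% COVID share to about 20–25% at 70–75%, and is nil without effect modification. These sizes rest on assumed control risks, odds ratios and COVID shares, none of which the documents supply.

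The confounding is not complete, because non-COVID patients can also be Extended-only. The primary analysis and the stopping rules are not affected. This is an error of interpretation in one subgroup that should be corrected before results are seen.

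**What to change.** Change the subgroup in one of two ways, in the protocol and the SAP:

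- estimate the treatment-by-enrolment-history interaction in a model that also contains a treatment-by-COVID interaction; or
- restrict the comparison to non-COVID Extended Cohort patients.

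In either case, restate the purpose: to assess whether the extension effect differs by how the initial course was given, under the Early Cohort protocol or as usual care.

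The edit is short and needs no new data. The cost is some precision. Restriction drops the COVID patients, and the number of non-COVID patients entering by the third route is unknown; the joint model keeps everyone. Neither option makes the groups randomised. Patients from the Early Cohort had to be within 72 hours of ICU admission and without an existing corticosteroid indication, and received a fixed 10-day course. The others may have had any corticosteroid at any initial dose for 8–12 days. The report should say that these differences limit what a remaining interaction can mean.

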### **Randomization Scheme**

We will randomize using an online centralized password-protected randomization system (REDCap) following a 1:1 schedule, stratified by study site and level of oxygen support (noninvasive, invasive or ECLS) at the time of randomization.

[figure not shown]
### **MINIMIZING SOURCES OF BIAS**

The online randomization system will ensure allocation concealment and employ variable block sizes. Patients and treating healthcare providers will not be blinded. While blinding is an important mechanism to mitigate performance and detection bias, blinding would not allow for subsequent randomization of those that receive dexamethasone in the Early Cohort to further randomization in the Extended Cohort, thereby eliminating our efficiency and ability to answer multiple questions within the same trial. We will mitigate outcome ascertainment bias by using relatively objective outcomes not easily influenced by knowledge of treatment assignment (e.g. mortality). We will blind data analysts and statisticians. For the few subjective outcomes (e.g., nosocomial infections), we will establish a blinded adjudication committee that will evaluate events using standardized and accepted definitions to limit risk of bias.

We will collect data related to co-interventions to evaluate whether lack of blinding leads to differential use of specific interventions or treatments and will provide protocols for ventilation, and supportive therapy best practices to help ensure consistency. We will also minimize bias by using an intention-to-treat analysis and minimizing loss to follow-up. Missing data will also be minimized through use of a clear and comprehensive data dictionary with online data entry using logical consistency rules.

---

---

## **DOCUMENTATION, RECORD ACCESS AND MAINTENANCE OF STUDY RECORDS**

### **Documentation of Participants Participation**

A statement acknowledging the participation of a participant in this clinical trial must be documented in the participant's medical records along with the signed ICF.

### **Regulatory Requirements**

The following documents are required for participating centres within Canada:

- All Investigators must complete and sign the Health Canada Qualified Investigator Undertaking form. The completed forms must be returned to Ozmosis Research Inc. prior to any drug shipment.
- Ozmosis Research Inc. will submit via fax or e-mail to Health Canada a completed Health Canada Clinical Trial Site Information Form after local activation of each participating Canadian centre.

[figure not shown]
The following documents are required for all participating centres:

- All applicable regulatory documents as listed in the Protocol Activation Checklist provided by Ozmosis Research Inc. to the sites.

### **Participant Confidentiality and Access to Source Data/Documents**

Any research information obtained about the participant in this study will be kept confidential. A participant will not be identified by name, only by his/her initials. The participant's name or any identifying information will not appear in any reports published as a result of this study.

However, information obtained from individual participant's participation in the study may be disclosed with his/her consent to the health care providers for the purpose of obtaining appropriate medical care. The participant's medical records/charts, tests will be made available to Ozmosis Research Inc., UHN, its potential eventual partners, the Canadian HPFB/PPD, the REB/IRB and any other regulatory authorities. This is for the purpose of verifying information obtained for this study. Confidentiality will be maintained throughout the study within the limits of the law.

A participant's name will not be given to anyone except the researchers conducting the study. All identifying information will be kept behind locked doors, under the supervision of the study Principal Investigator and will not be transferred outside of the hospital.

A participant may take away his/her permission to collect, use and share information about him/her at any time. If this situation occurs, the participant will not be able to remain in the study. No new information that identifies the participant will be gathered after that date. However, the information about the participant that has already been gathered and transferred may still be used and given to others as described above in order to preserve the scientific integrity and quality of the study.

### **Confidentiality of the Study**

[figure not shown]
Data generated as a result of this study are to be available for inspection on request by local health authority auditors, the Sponsor's Study Monitors and other personnel (as appropriate) and by the IRB/EC. The Investigator shall permit sponsor, authorized agents of the sponsor, CRO and regulatory agency employees to enter and inspect any site where the drug or records pertaining to the drug are held, and to inspect all source documents. The protocol and other study documents contain confidential information and should not be shared or distributed without the prior written permission of sponsor.

### **Registration of Clinical Trial**

Prior to the first participant being registered/enrolled into this study, the Sponsor will be responsible for ensuring that the clinical trial is registered appropriately to remain eligible for publication in any major peer-reviewed journal, adhering to the guidelines put forth by the International Committee of Medical Journal Editors (ICMJE).

### **Maintenance of Study Records**

To enable evaluations and/or audits from Regulatory Authorities, Ozmosis Research Inc. or the Sponsor, the Investigator agrees to keep records, including the identity of all participants (sufficient information to link records, eCRFs and hospital records), all original signed informed consent forms, copies of all source documents and detailed records of treatment disposition. The Investigator should retain these records for 15 years after study close-out as required by Canadian regulations or as specified in the Clinical Trial Agreement, whichever is longer.

---

If the investigator relocates, retires, or for any reason withdraws from the study, then the Sponsor should be prospectively notified. The study records must be transferred to an acceptable designee, such as another investigator, another institution, or to the Sponsor. The investigator must obtain the Sponsor's written permission before disposing of any records.

## **PUBLICATION POLICIES AND DISCLOSURE OF DATA**

[figure not shown]
This section is in accordance with the PRACTICAL master trial.

### **Intellectual Property**

Intellectual property guidelines will conform with UHN Policy for Principal Investigator.

### **Data Sharing**

Please refer to PRACTICAL Master Protocol for details.

[figure not shown]

